In this study, the placebo will consist of inactive tablets identical to the active treatment tablets. Treatment assignments (active drug versus placebo) will be randomized for each patient to the two treatment periods within each block. (see Section F.1.6 for details about the randomization process; the unblinded randomization schema is available to unblinded study team members in Appendix I.

This study is part of Early-Phase Pain Investigation Clinical Network (EPPIC-Net), under The Helping to End Addiction Long-termSM Initiative, or NIH HEAL InitiativeSM.

D. 2. Study Endpoints

D.2.1. Primary Safety Endpoint

The primary safety endpoint is the incidence of treatment emergent adverse events (TEAEs), reported between the administration of study drug on Day 1 and the completion of the study at Week 24 or Early Termination.

D.2.2. Primary Efficacy Endpoint

The primary efficacy endpoint is pain in the index knee, measured weekly using the WOMAC-A (Pain subscale), (Bellamy et al, 1988). We will use the numerical rating scale version of the WOMAC-A, with the subject assessing each of 5 questions using an 11-point (0 to 10) scale; the total score is the sum of the individual item scores (range 0-50). A higher WOMAC-A score represents worse symptom severity.

All WOMAC subscales show strong evidence of validity and reliability (Salafi et al, 2003), and are the most frequently used primary endpoints for OA trials because of their strong assay sensitivity (Jung et al, 2018). Assessments during the last 2 weeks of each treatment period will be used to test the primary hypotheses in order to avoid possible carryover effects of unknown duration. All weekly measurements of WOMAC-A will be used to study the course of OA pain symptoms during treatment, including onset of action and carryover effects.

D.2.3. Secondary Endpoints

The following measures are considered secondary outcomes related to pain due to OA of the knee. They will be assessed at Baseline and at study visits through Week 24. See Section F.1.1 Schedule of Events for full description of procedure timepoints. The Daily Knee Pain Intensity on a 0-10 NRS which will be recorded daily the week prior to each study visit. For a full description of secondary endpoint scales and assessments, see Section F.2.4 and F.2.5.

- Daily Knee Pain Intensity on a 0-10 Numeric Rating Scale (NRS).
- WOMAC-C (Function subscale)
- Hospital Anxiety and Depression Scale (HADS)

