experiencing an SAE will be seen by the investigator or designee as soon as is feasible following the report of the SAE.

SAEs that occur after the study follow-up period should be reported if in the judgment of the investigator there is “a reasonable possibility” that the event may have been caused by the product.

F.4.8.3. Unanticipated Problem Reporting

An unanticipated problem is any incidence, experience, or outcome that is:

- Unexpected (in terms of nature, severity, or frequency) given the information provided in research-related documents and the characteristics of the subject population being studied;
- Related or possibly related to participation in the research; and
- Suggests that the research places subjects or others at a greater risk of harm than was previously known or recognized.

Advarra uses the following to determine whether something is an unanticipated problem involving risk to subjects or others:

- Unanticipated or unexpected at the time of IRB approval;
- Involved new or increased risk to subjects or others; and
- Related to the research.

F.4.8.4. Elective Procedures and Surgeries

As a part of consenting, subjects are asked to affirm that are not planning to have any surgeries, invasive procedures, or IA injections of the index knee or any surgeries/procedures that are otherwise contraindicated during their participation in the study (exclusion criterion #10).

For the purposes of this protocol, the following conventions will apply for SAE reporting of elective procedures and surgeries:

- A prescheduled elective procedure or a routinely scheduled treatment is not to be considered an SAE, even if the subject is hospitalized, provided the site stipulates that:
 - The condition requiring the prescheduled elective procedure or routinely scheduled treatment was present before and did not worsen or progress between the subject’s consent to participate in the clinical trial and the time of the procedure or treatment.
 - The prescheduled elective procedure or routinely scheduled treatment is the sole reason for admission and intervention.
- An untoward medical event occurring during the pre-scheduled elective procedure or routinely scheduled treatment should be recorded as an AE or an SAE. Any concurrent medications should also be recorded on the eCRF.

F.4.8.5. Other Reportable Information

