A patient who remains in the study for the first two treatment periods or for all four treatment periods will receive a balanced exposure to treatments randomized to receive. If patients discontinue treatment prior to completing the entire 24 weeks of study, all their data (including weekly assessments) from their time in the study will be used in the analyses. Because the main analysis is based on maximum likelihood estimation using a mixed-effects multi-period crossover model, the inferences will be unbiased under missing at random assumptions. No imputation of missing data is planned for this study, unless intensive investigations indicate that reliable and valid data imputation is possible, in which case multiple imputation will be performed and the analysis of the imputed data sets will serve as a sensitivity check of the results from the primary analysis based on the mixed-effects models (van Buuren et al, 2011).

All analyses will adjust for age, sex, K-L grade, and site.

All hypothesis tests will be two-sided using 5% significance level, and *p*-values unadjusted for multiple testing will be reported. The justification for this decision is that this is a Phase II investigation and all assessed outcomes are of specific and unique interest. Much more important than testing hypotheses is the efficient estimation of all quantities of interest, and this will be carried out throughout the analyses. Point estimates, 95% confidence intervals and standardized effect sizes (e.g., Cohen's *d*) will be reported for all estimated effects, regardless of whether the null hypotheses were rejected or not.

K.2. Hypothesis testing

Aim 1: Assess the safety of CNTX-6970 (300mg BID).

There will be no formal hypothesis testing under Primary Study Aim 1. All AEs and SAEs observed during different treatment periods will be summarized based on severity and relation to the active treatment (CNTX-6970 300mg BID). The reports will include tabulation of the AEs and SAEs by period, block, and treatment; point estimates and 95% CIs will be reported. Similarly, we will summarize relevant laboratory measures (see Section F.2.1) with appropriate estimates.

Aim 2: Assess the efficacy of CNTX-6970 (300mg BID) in comparison to placebo with respect to the primary outcome measure for pain due to osteoarthritis of the knee - WOMAC Part A.

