WOMAC Part A (WOMAC-A) assessed only in the last two weeks of each 6-weeks treatment period will be used for this primary analysis in order to avoid any carryover effects, which are expected to vanish after 4 weeks; the specific carryover effect of the two doses of CNTX-6970 will be studied under Aim 3.

HYPOTHESIS 1: CNTX-6970 300mg BID is superior to placebo with respect to symptoms measured by WOMAC Part A.

The hypothesis testing is based on the WOMAC-A assessed only in the last 2 weeks of each 6-week treatment period. This provides a more than adequate 4-week washout interval. The adequacy of this 4-week period is based on extensive pharmacokinetics (PK) and pharmacodynamics (PD) of the study agent. The PK/PD analyses were performed for single dose and multiple ascending dose (MAD) studies using both QD and BID dosing regimens. For the single dose study, the PK study showed that the mean half-life ranged from 15.8 to 16.6 hours. For PD, the CNTX dossier reports that "... based on the half-life of CNTX-6970 determined in humans it is estimated that the duration of the PD may be between 8-12 hours." Specifically, after two doses of 300mg the plasma level is 10ng/ml 36 hours after dosing. The PD effect is less than 50% at 10ng/ml based on the MCP-1 interaction with CCR2. Hence, we anticipate a more than adequate washout period. Additionally, under Aim 6 (see below), we explicitly study the potential carryover effects in the statistical modeling. The statistical models will utilize a standard approach to adjust for carryover effects in a multi-period crossover design when estimating treatment effects, and allows for testing for the existence of carryover effect (Chen and Chen, 2014).

Aim 3: Assess the efficacy of CNTX-6970 (300mg BID) in comparison to placebo with respect to secondary outcome measures related to OA of the knee: (a) WOMAC-C (function subscale), (b) Hospital Anxiety and Depression Scale (HADS), (c) Patient Global Impression of Change (PGIC), (d) PROMIS Sleep Disturbance Scale – 6A, (e) Sleep Duration Question, and (f) Daily Knee Pain Intensity on a 0-10 NRS.

HYPOTHESIS 2: CNTX-6970 300mg BID is superior to placebo with respect to symptoms measured by (a) WOMAC-C (function subscale), (b) Hospital Anxiety and Depression Scale (HADS), (c) Patient Global Impression of Change (PGIC), (d) PROMIS Sleep Disturbance Scale– 6A, (e) Sleep Duration Question, and (f) Daily Knee Pain Intensity on a 0-10 NRS.

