## 5 Study Methods

### 5.1 General Study Design and Plan

This is a multi-crossover design with 2 blocks and 2 periods per block. Each period lasts 6 weeks. Patients will be randomized to one of the treatment sequences shown in Figure 1. The Schedule of Events Table in

the Protocol gives the timing of the outcome assessments. In general, we will be analyzing the data on an intent-to-treat basis (ITT).

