## 5.3 Randomization and Blinding

For entry into the study and randomization, all eligibility criteria MUST be met (i.e., all inclusion criteria and no exclusion criteria specified in the protocol). Patients who meet inclusion/exclusion criteria at the Baseline Visit (day 0) will be randomized. After documentation of written informed consent and the screening period, clinical sites will confirm eligibility and complete randomization by accessing the Almac's centralized web-based system for randomization and drug management - the Interactive Web Response System (IXRS). Subjects will be randomized equally between treatment sequences shown in Figure 1: Drug:Placebo:Placebo:Drug or Placebo:Drug:Drug:Placebo. A standard block randomization will be used, stratifying by K-L grade (stratum 1 K-L grade 1 or 2, and stratum 2 K-L grade 3 or 4) to achieve balance on randomization sequences. The randomization will be implemented by the IXRS vendor in consultation with the study statisticians. After Randomization, drug will be dispensed.

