## 8 Safety Analyses

A primary objective of this trial is to evaluate the safety of CNTX-6970 300 mg BID for the treatment of pain related to OA of the knee compared to placebo. The primary safety endpoint is the incidence of treatment emergent adverse events (TEAEs), reported between the administration of study drug on Day 1 and the completion of the study at Week 24.

**Aim 1:** Assess the safety CNTX-6970 (300 mg BID).

There will be no hypothesis testing under Aim 1. All AEs and SAEs observed during different treatment periods will be summarized based on severity and relation to the active treatment (CNTX-6970 300mg BID). The reports will include tabulation of the AEs and SAEs by period, block, and sequence; point estimates and 95% CIs will be reported. Similarly, we will summarize relevant laboratory measures which include chemistry and Complete Blood Count (CBC) with appropriate estimates.

The primary safety endpoint is the incidence of treatment emergent adverse events (TEAEs), reported between the administration of study drug on Day 1 and the completion of the study at Week 24 or Early Termination. Specifically, the primary safety endpoint for the study is the following: Percent of adverse events and serious adverse events in the final 2 weeks of each treatment period. Vital signs (heart rate, blood pressure, etc.) will be obtained regularly throughout the study at the time of study visits. Height and weight will be collected during the screening period and at the subject's final study visit. Blood chemistry and hematology panels will also be obtained regularly at study visits. All ECGs will be documented by recording date, time, heart rate, QRS duration, PR interval, RR interval, QT, and QTcF on the eCRF. Paper strips will be maintained in the patient file. If indicated, additional ECG assessments can be made at the discretion of the investigator.

The severity of each AE will be graded on a 4-point scale and reported in detail as indicated on the eCRF. Vital signs, systemic effects, and laboratory abnormalities will be graded using the Toxicity Grading Scale

for Healthy Adult and Adolescent Volunteers Enrolled in Preventive Vaccine Clinical Trials, available at <https://www.fda.gov/media/73679/download> (See MOP Appendix M).

- Grade 1 (Mild: No interference with activity)
- Grade 2 (Moderate: Some interference with activity, not requiring medical attention)
- Grade 3 (Severe: Prevents daily activity and requires medical intervention)

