### 9.1 Primary Efficacy Analysis

For the efficacy Aim 2, data from the WOMAC Part A (WOMAC-A) assessed only in the last two weeks of each 6-weeks treatment period will be used for this primary analysis in order to avoid any carryover effects, which are expected to vanish after 4 weeks. Hypothesis 1 in Section 4 will be tested using the following random-effects multi-period crossover model that employs block and period effects to compare the active treatment to placebo (Zucker *et al.*, 1997; Chen and Chen, 2014). Specifically, the model is:

$$y_{i(s)jkm} = \beta_0 + \gamma_j + \delta_k + \beta_1 X_{i(s)jk} + \beta_2' \mathbf{w}_{i(s)} + b_s + b_{i(s)} + \epsilon_{i(s)m}, \quad (1)$$

where  $i(s)$  is the index for patient  $i$  at site  $s$ ;  $\beta_0$  is the intercept;  $j$  is the index for block,  $j = 1, 2$  and  $\gamma_j$  is the block effect;  $k$  is the index for period,  $k = 1, 2$ , and  $\delta_k$  is the period effect;  $m$  is the measurement time;  $y_{i(s)jkm}$  is the primary outcome for subject  $i(s)$ , block  $j$ , period  $k$ , time  $m$ ;  $\beta_1$  represents the treatment effect, and  $X_{i(s)jk}$  is an indicator for active treatment ( $X_{i(s)jk} = 1$ ) or placebo ( $X_{i(s)jk} = 0$ ) for patient  $i(s)$ , in block  $j$ , during period  $k$ ;  $\mathbf{w}_{i(s)}$  is a vector of baseline characteristics (e.g., age, sex, K-L grade indicator) for patient  $i(s)$  and  $\beta_2$  is a vector of coefficients for those baseline characteristics;  $b_s \sim N(0, \sigma_{site}^2)$  is a random site effect and  $b_{i(s)} \sim N(0, \sigma_b^2)$  is a subject-level random effect (nested within site);  $\epsilon_{i(s),m}$  is a random error with an  $AR(1)$  structure:  $\epsilon_{i(s),m} = \phi \epsilon_{i(s),m-1} + u_{i(s)m}$ , with  $u_{i(s)m} \sim N(0, \sigma_u^2)$ . The subject-level random effects will model the repeated measures within subjects. The block and period effect terms will accommodate changes in mean pain scores across blocks and periods of the design.

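### No adverse-event contact is scheduled after Week 24, when half the patients are still on active drug, and no rule covers events starting just after a drug-to-placebo switch

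*Protocol*

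**What the plan says.** - **Window.** Protocol D.2.1 defines the primary safety endpoint as the incidence of TEAEs "reported between the administration of study drug on Day 1 and the completion of the study at Week 24 or Early Termination". SAP 8 uses the same window. SAP 4.4.1 does too, but closes it early when the patient discontinues treatment.
- **Last contact.** Visit 9 (Week 24/ET) is the final entry in the Schedule of Events and in Protocol F.1. Protocol F.4.8.2.1 nevertheless says "SAEs that occur after the study follow-up period should be reported", provided the investigator considers a drug cause reasonably possible. No follow-up period appears in the schedule.
- **Design.** SAP 5.3: "Subjects will be randomized equally between treatment sequences shown in Figure 1: Drug:Placebo:Placebo:Drug or Placebo:Drug:Drug:Placebo". SAP 5.1: "Each period lasts 6 weeks". No drug-free interval between periods is described. Protocol F.1.13 has dosing confirmed twice daily between Weeks 21 and 24, and F.2.2.1 places the Week 24 PK sample at steady state.
- **Persistence.** Protocol K.2 (Aim 2) reports from single dosing that "the PK study showed that the mean half-life ranged from 15.8 to 16.6 hours", and cites an estimated pharmacodynamic duration of 8 to 12 hours. For efficacy, SAP 9.1 uses only the last two weeks of each period to avoid carryover effects, "which are expected to vanish after 4 weeks".
- **Tabulation.** Protocol K.2 (Aim 1): "The reports will include tabulation of the AEs and SAEs by period, block, and treatment". SAP 8: "The reports will include tabulation of the AEs and SAEs by period, block, and sequence". Neither gives a lag or attribution rule.
- **Second definition.** Protocol F.2.7 and SAP 8 also define the primary safety endpoint as the percentage of AEs and SAEs in the closing two weeks of each period.

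**The concern.** Safety is part of the primary objective (Aim 1). K.2 describes earlier single- and multiple-dose studies, and Protocol C gives 10 days as the earlier exposure to this dose; here patients take it for 6 weeks at a stretch, or 12 consecutive weeks in Placebo:Drug:Drug:Placebo. Yet for half the patients the AE window shuts at about the time of the last active dose, so a new non-serious event a day or two later has no route into the database.

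A related weakness arises at each drug-to-placebo switch. If AEs are tabulated by the treatment of the period in which they start, an event the next morning falls under placebo although drug is still present. That moves the comparison towards no difference. The efficacy analysis has an explicit buffer against carryover; under the Day 1 to Week 24 definition the safety analysis has none.

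**Working it through.** **1. The plan's own figure.** The documents give no figure for a post-dose AE window. The related figure is the number completing all four periods at 15% early termination per period:

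- SAP 6: 55 × 0.85⁴ = 28.7 (stated: about 29).
- Protocol K.4: 50 × 0.85⁴ = 26.1 (stated: 26).

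Both reproduce.

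**2. Patients ending on drug.** With 1:1 allocation, 55/2 = 27.5, so 27 or 28 of those randomised have drug in period 4. Among completers it is 29/2 = 14.5, so about 14 or 15.

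**3. Length of the exposed window.** The number of half-lives is an assumption. I use 5, with 3 and 7 as the range.

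- 5 × 15.8 h = 79 h = 3.3 days; 5 × 16.6 h = 83 h = 3.5 days.
- 3 × 15.8 h = 47.4 h = 2.0 days; 7 × 16.6 h = 116.2 h = 4.8 days.

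**4. Unobserved after Week 24.** A completer has 2 × 42 = 84 drug days and 84 placebo days. Half the patients lose the tail, so the average loss relative to planned drug time is 0.5 × 3.46/84 = 2.1% (0.5 × 3.29/84 = 2.0% at the shorter half-life).

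**5. Credited to placebo after a switch.** Each sequence has one drug-to-placebo switch: at Week 6 in Drug:Placebo:Placebo:Drug and at Week 18 in Placebo:Drug:Drug:Placebo. Let f = days of persistence/84. In the worst case the full on-drug AE rate applies throughout the tail. The observed placebo rate is then r_P + f(r_D − r_P), the rate difference kept is 1 − f, and the observed rate ratio is RR/[1 + f(RR − 1)].

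| Persistence | f | Difference kept | True RR 2 seen as | True RR 3 seen as |
|---|---|---|---|---|
| 12 h (upper stated PD duration) | 0.6% | 99.4% | 1.99 | 2.96 |
| 3.29 days (5 × 15.8 h) | 3.9% | 96.1% | 1.92 | 2.78 |
| 3.46 days (5 × 16.6 h) | 4.1% | 95.9% | 1.92 | 2.77 |
| 4.84 days (7 × 16.6 h) | 5.8% | 94.2% | 1.89 | 2.69 |
| 28 days (efficacy carryover bound) | 33% | 66.7% | 1.50 | 1.80 |

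**6. Check on the remedy.** Suppose post-switch events are moved to active but their days are not. For an inert drug with a constant event rate, the active:placebo event ratio becomes (84 + 3.5)/(84 − 3.5) = 87.5/80.5 = 1.09 with a 3.5-day lag, and 112/56 = 2.0 with a 28-day lag. A lag rule must therefore move exposure days with the events and report rates.

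**The case against.** Four arguments on the other side carry weight.

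- **The final-two-weeks definition.** Under Protocol F.2.7 and the matching sentence in SAP 8, an event just after a switch counts for neither treatment, which is the same four-week buffer that efficacy has. This stands: no text says such events count as placebo, and that follows only from the K.2 tabulation. But this definition contradicts D.2.1, does not count the event as active either, and leaves the gap after Week 24 open.
- **Existing safety provisions.** SAEs thought possibly drug-related stay reportable after the study. F.4.8.2.1 has patients telephone the investigator about any SAE. F.4.1 requires AEs to be resolved or stable at study end, and F.4.7.3 follows patients withdrawn for an AE. F.3.2 seeks data up to a period-end visit from those who stop drug but keep consent. So it would be wrong to infer that AE collection ends completely. What these leave uncovered is a new, non-serious event after the last active dose. The Manual of Procedures was not available and might say more.
- **Lost time is not bias.** Unobserved days add neither events nor person-time, so they do not attenuate an on-drug rate. Every completer is also observed for at least six weeks after one drug-to-placebo switch. This stands: the Week 24 gap is missing information, and only the switch problem biases the rate comparison.
- **Size.** Aim 1 has no hypothesis test and about 29 completers are expected, so a 4% shrinkage is far below sampling error. This also stands.

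A reader might further infer that tabulating by sequence, as SAP 8 says, cannot reveal a drug effect because each sequence holds 12 weeks of drug and 12 of placebo. The documents do not support that. Each period-by-block-by-sequence cell contains exactly one treatment, and SAP 4.1.1 promises frequencies for active and placebo. What remains is a wording difference between SAP 8 and Protocol K.2.

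**Conclusion.** The point holds as a collection gap with a small attribution bias. Half the randomised patients are scheduled to take active drug up to the last contact, which leaves about 3.3 to 3.5 days at five half-lives in which new non-serious events are not collected. Under tabulation by period and treatment, misattribution at switches shrinks the rate difference by about 4% at worst (2.4% to 5.8% for 3 to 7 half-lives).

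This rests on dosing continuing to Visit 9, on the single-dose half-life applying at steady state, and on the full on-drug AE rate persisting through the tail, which overstates the bias. It also uses the two sequences in SAP 5.3. If Protocol D.1 (order randomised within each block) allowed all four sequences, half would still end on drug. Switches would average (2 + 1 + 1 + 1)/4 = 1.25 per patient, giving 1.25 × 3.46/84 = 5.1%.

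The 33% in the last table row should not be read as an expected bias. It needs the full on-drug AE rate to last 28 days, whereas Protocol K.2 describes four weeks as a more than sufficient washout and cites a pharmacodynamic duration in hours. Protocol D.2.2 does call the duration of carryover unknown, so a longer tail is possible but not established. Scheduled laboratory tests and ECGs are little affected, because the first after a switch comes three weeks later.

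The change is worth making because it is cheap and closes a real gap in safety data, not because the present tables would mislead badly.

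**What to change.** 1. **Collection.** Add one telephone AE contact for every patient after the last dose, early terminators included, at least about five half-lives later; the sponsor sets the exact interval. Extend the TEAE window in Protocol D.2.1, SAP 4.4.1 and SAP 8 to that contact, and align the follow-up wording in F.4.8.2.1 with it.
2. **Attribution.** In SAP 8, tabulate AEs by treatment at onset, consistent with Protocol K.2 and SAP 4.1.1. Add a sensitivity table that assigns to active both the events and the exposure days within a stated lag after each drug-to-placebo switch, reported as rates per person-time.
3. **Definition.** In the same edit, reconcile the two primary safety endpoint definitions (Day 1 to Week 24, or the last two weeks of each period) so that one is primary.

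The cost is one short call per patient by existing staff, a small protocol amendment and a few more table lines. Because every patient is called, the blind is not affected.
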